7.1.6 Imputation of Missing Data

Sensitivity analysis will be performed using multiple imputation (MI) for the primary and secondary endpoints. Missing data will be imputed based upon the observed data for each outcome under the MAR assumption following the paradigm first developed by Rubin (Shafer, 1999). The imputation will adjust for the outcome's baseline data in a regression model with data

imputed independently for each timepoint. A total of 10 imputation datasets will be created and analyzed based upon accepted convention (Shafer, 1999). Error estimates of the multiple imputation itself, as well as an overall summary of the efficacy analysis, will be averaged across the 10 imputed datasets based upon Rubin's paradigm.

Specifically, let Q denote the imputed mean of an efficacy outcome Y subject to missing data at a given timepoint, where the estimate of that mean for any i^{th} imputation would be defined as function of both observed and missing such that

$$\widehat{Q^{(i)}} = E\left(Q^{(i)}|Y_{observed}, Y_{missing}^{(i)}, Y_{Baseline}, I(Group)\right), i = 1, \dots, 10.$$

After all 10 datasets have been imputed, the overall estimate of Q is a simple average defined as

$$\bar{Q} = \frac{\sum_{i=1}^{10} \widehat{Q^{(i)}}}{10}.$$

For this analysis using 10 imputed datasets, the variance of \bar{Q} is defined as

$$Var(\bar{Q}) = 1.1B + \bar{U}$$

where B is the between imputation variance and U is the within imputation variance:

$$B = \frac{1}{9} \sum_{i=1}^{10} \left(\widehat{Q^{(i)}} - \bar{Q} \right)^2;$$

$$\bar{U} = \frac{\sum_{i=1}^{10} U^{(i)}}{10}.$$

PROC MI in SAS® will be used to impute missing data assuming missingness is monotone in pattern. If a subject is missing a baseline record causing non-monotone missingness, all non-missing post-baseline records will temporarily be set to missing as well. After the 10 imputation datasets are created, the non-missing post-baseline will be merged back in, thus creating complete datasets where only the originally missing records were imputed. Imputations will be performed with a seed of 469010.

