7.1.2 Mixed-Effects Model for Repeated Measures

A mixed-effects model for repeated measures (MMRM) will be used to evaluate Pain NRS, WOMAC, and Patient Global Assessment outcome measures. The null hypothesis is that the mean difference in the endpoints between the two treatment groups is zero, versus the alternative hypothesis that this difference is not zero. The hypotheses can be expressed as follows:

$$H_0: (\beta_1 - \beta_0)_t = 0$$

$$H_A: (\beta_1 - \beta_0)_t \neq 0,$$

where β_0 refers to the least squares mean change from baseline in the placebo group and β_1 refers to the least squares mean change from baseline in the active treatment group, evaluated at timepoint t .

For Pain NRS, the model will be estimated assuming a Toeplitz variance-covariance matrix. The Toeplitz structure is a more generalized form of autoregressive-1 (AR1) structure, allowing the data to inform how the correlation between within-subject observations decreases over time instead of implicitly defining a uniform decay structure (Kincaid, 2005).

For WOMAC and Patient Global Assessment, the model will be estimated assuming an unstructured variance-covariance matrix, allowing the data to fully inform the correlation between within-subject observations (Kincaid, 2005).

MMRM presumes that missing data are not caused by something observable within the conduct of the trial (i.e. missing-at-random [MAR]). It is plausible to presume a MAR mechanism as there have been no observed tolerability issues to the administration of study injection during the prior development trials. Additionally, the study injection cannot be removed after it has been administered, eliminating study drug discontinuation as a source of treatment estimate confounding.

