7.1.6.1 Tipping Point Analysis

The MI paradigm, as proposed by Rubin, does not require nor assume any specific assumption about the nature of the missing data. Further, imputations can be (theoretically) created under any assumption of missing mechanism. A two-way tipping point analyses will be conducted to evaluate the robustness of the analyses with MI under the MAR assumption. With the tipping point approach, several additional MI datasets are created, each departing slightly from the assumptions used in the original analysis. The intended result is to establish a certain point in which the new shifted imputations have “tipped”, or overturned, the original conclusions from the original analysis (i.e. a statistically significant result is now not statistically significant). The magnitude of the shift required to tip the analysis is then evaluated for plausibility; an

implausible shift will lead to the conclusion that the MI analysis is robust to departures from MAR assumption.

The tipping point exercise will be conducted only for MI analysis(es) that is/are statistically significant under the MAR assumption. Applicable MI analyses will be reassessed by shifting the imputed values for the treatment group by intervals of ± 0.5 for Pain NRS and ± 5 for WOMAC and Patient Global. An implausible shift parameter would be higher in magnitude than the observed difference in mean change in the associated outcome between the treatment and placebo groups.

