7.3 Efficacy Assessments

7.3.1 Pain NRS

The Pain NRS is an 11-point scale [0-10] for subject self-reporting of average knee pain in the previous 24 hours, where 0 represents no pain and 10 represents extreme pain. Subjects were prompted to report average pain in both knees daily on their electronic device (between 5:00 pm and 11:59 pm) during the screening period and on the target knee only starting from Day 1 through the end of the study. An average weekly score (referred to as Pain NRS) was calculated for each subject if they had provided a response for at least 4 out of 7 days in a given week. Weeks are defined as Day -7 through Day -1 (day before treatment) for baseline, Day 1 (day of treatment) through Day 7 for Week 1, Day 8 through Day 14 for Week 2, and so on as detailed in [Appendix 1](#). The day on which subjects completed their scheduled study visits (e.g. Week 4 Visit, Week 12 Visit, etc.) does not impact the above definition of weeks.

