9.2 Primary Efficacy Analysis

9.2.1 Main Analysis

Change over time in Pain NRS will be characterized using an MMRM model to estimate change from baseline with treatment group, week, treatment \times week interaction and baseline value as covariates. The model will include all timepoints for subjects in the FAS and will be evaluated at Week 12.

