15.3 Appendix 3 – Estimands

Primary	Estimator	Variable	Population	Intercurrent events	Population level summary
	Main	Change from baseline in Pain NRS at Week 12	FAS	1) Prohibited medications: treatment policy strategy; analysis will be conducted regardless of use of prohibited medications. 2) NSAID/acetaminophen: treatment policy strategy; analysis will be conducted regardless of change in NSAID/acetaminophen regimen.	Difference in the change from baseline between SM04690 and placebo using MMRM with treatment group, week, treatment × week interaction and baseline value as covariates.
	Sensitivity 1	Change from baseline in Pain NRS at Week 12	FAS	1) Prohibited medications: treatment policy strategy; analysis will be conducted regardless of use of prohibited medications. 2) NSAID/acetaminophen: treatment policy strategy; analysis will be conducted regardless of change in NSAID/acetaminophen regimen.	Difference in the change from baseline between SM04690 and placebo using baseline-adjusted ANCOVA with missing data imputed using the MI method; followed by tipping point analysis.
	Sensitivity 2	Change from baseline in Pain NRS at Week 12	FAS	1) Prohibited medications: treatment policy strategy; analysis will be conducted regardless of use of prohibited medications. 2) NSAID/acetaminophen: composite strategy; the use of NSAIDs/acetaminophen will be considered in the analysis by adding change from baseline in Total NSAID Score at the corresponding week as a covariate to the analysis model.	Difference in the change from baseline between SM04690 and placebo using baseline-adjusted ANCOVA with change in Total NSAID Score as a covariate.
	Sensitivity 3	Change from baseline in Pain NRS at Week 12	PPAS	1) Prohibited medications: principal stratum strategy; subjects who used prohibited medications will be excluded from this analysis. 2) NSAID/acetaminophen: treatment policy strategy; analysis will be conducted regardless of change in NSAID/acetaminophen regimen.	Difference in the change from baseline between SM04690 and placebo using baseline-adjusted ANCOVA. By definition, the PPAS will not include subjects with missing data.

	Estimator	Variable	Population	Other intercurrent events	Population level summary

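### The multiple imputation in SAP 7.1.6 uses only baseline and ignores observed post-baseline scores, so Sensitivity 1 and its tipping point rest on a stricter missing-data assumption than the MMRM they support

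*SAP*

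**What the plan says.** SAP 7.1.6 describes the imputation model in one sentence, which begins "The imputation will adjust for the outcome's baseline data in a regression model with data" and continues "imputed independently for each timepoint. A total of 10 imputation datasets will be created and analyzed based upon accepted convention". Baseline is the only predictor named there. The displayed formula also conditions on a group indicator, and its observed-data term refers to the outcome at the given timepoint, so it does not bring in other visits. The variables to be given to PROC MI are not listed. The only non-monotone case treated is a missing baseline: "If a subject is missing a baseline record causing non-monotone missingness, all non-missing post-baseline records will temporarily be set to missing as well". That is the only such case possible in a model of baseline plus one timepoint, so it fits the same reading.

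The main analysis works differently. For Pain NRS, "the model will be estimated assuming a Toeplitz variance-covariance matrix" (SAP 7.1.2), and "The model will include all timepoints for subjects in the FAS and will be evaluated at Week 12" (SAP 9.2.1). WOMAC and Patient Global use an unstructured covariance matrix.

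Sensitivity 1 in SAP Appendix 3 is the treatment difference "using baseline-adjusted ANCOVA with missing data imputed using the MI method; followed by tipping point analysis". Under SAP 7.1.6.1 the tipping point is run only where the imputed analysis is significant. It shifts the imputed values of the treatment group in steps of 0.5 (Pain NRS) or 5 (WOMAC and Patient Global).

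**The concern.** The MMRM allows missingness to depend on any observed score. Imputation from baseline and group alone requires that, given those two, missingness does not depend on post-baseline scores at all. The sensitivity analysis therefore makes a stronger assumption than the analysis it is meant to support.

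The discarded information is substantial here. Pain is recorded daily, so a subject lost just before Week 12 can have up to 11 observed weekly averages. A weekly average exists only "if they had provided a response for at least 4 out of 7 days in a given week" (SAP 7.3.1), so a subject with three diary days in Week 12 and complete neighbouring weeks is imputed without those weeks. Protocol 5.6.1 lists lack of efficacy as a reason for discontinuation, so missingness related to observed pain is foreseeable.

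Sensitivity 1 and its tipping point are the plan's only missing-data analyses. Sensitivity 2 concerns the NSAID score and Sensitivity 3 is the per-protocol set. If Sensitivity 1 differs from the MMRM, the reader cannot tell whether the MMRM is fragile or the imputation discarded relevant data. If a shift toward zero makes the imputed analysis non-significant, the tipping point is not run, even if the MMRM is significant.

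**Working it through.** **Inputs from SAP section 5 (re-estimated sample size).** Pain NRS difference -0.80; baseline SD 1.2; follow-up SD 2.4; baseline to follow-up correlation 0.25; 225 evaluable of 250 per arm; 10% dropout. The documents give no between-week correlation and no dropout mechanism, so both are assumed below and shown as ranges.

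**1. The plan's own figure.** SE = 2.4 × √(1 − 0.25²) × √(2/225) = 2.4 × 0.968 × 0.0943 = 0.219. Power = Φ(0.80/0.219 − 1.96) = Φ(1.69) = 95.5%. The SAP's 1,000 simulations gave 94.3%, which is close enough.

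**2. Information discarded.** Baseline explains 0.25² = 6.25% of Week 12 variance. Add one observed week with correlation r to Week 12 and 0.25 to baseline: R² = (0.25² + r² − 2 × 0.25² × r)/(1 − 0.25²). This gives 27%, 50% and 81% for r = 0.5, 0.7 and 0.9.

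Example: a placebo subject with the average baseline of 6.0 drops out after an observed weekly pain of 8. The expected Week 12 imputation under 7.1.6 is the placebo mean, 3.8. Using the observed week (same mean and SD assumed) it is 3.8 + [(r − 0.0625)/0.9375] × (8 − 3.8) = 5.8, 6.7 and 7.6.

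**3. What Sensitivity 1 estimates.** Imputed values are drawn from a regression on baseline and group fitted to the observed cases. The ANCOVA then refits that regression, so in expectation it returns the complete-case coefficient. Check: 1,500 simulated trials, 250 per arm, 10% missing at random, 10 imputations, Rubin's rules. The imputed analysis gives -0.803 (SE 0.220) and complete-case ANCOVA gives -0.803 (SE 0.219). The two estimates correlate at 0.995, and power is 94.6% for both.

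**4. Size of the shift.** Large-sample simulation, 150,000 per arm, 12 weekly averages, between-week correlations declining toward 0.50, 0.62 or 0.72. Dropout depends on the last observed week, with 10% missing at Week 12. The table gives the absolute gap, in points, between the planned imputation (group included) and a fitted Toeplitz MMRM:

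| Log-odds of dropout per pain point | Same mechanism in both arms (toward zero) | One arm only (either direction) |
|---|---|---|
| 0.2 | 0.00–0.01 | 0.06–0.09 |
| 0.4 | 0.02–0.05 | 0.12–0.17 |
| 0.6 | 0.03–0.085 | 0.17–0.23 |

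With random missingness the gap is at most 0.003. In the one-arm case, pain-driven dropout on placebo moves the estimate toward zero; on active it moves it away.

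A simpler model (baseline, Week 8 and Week 12; 1,000,000 per arm; r from 0.5 to 0.9; dropout driven by Week 8 pain) gives 0.005–0.075 for both arms and 0.05–0.24 for one arm. Adding Week 8 to the imputation brings the estimate within 0.002 of the full-data value. That recovery is by construction, because dropout there depends only on observed values.

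Two variants bound this. If dropout depends on pain relative to the subject's own arm mean, equally in both arms, there is no shift. If the mechanism runs in opposite directions in the two arms, more extreme still, the baseline-only estimate is -0.62, -0.53 and -0.43 at r = 0.5, 0.7 and 0.9 (slope of 1 log-odds per SD).

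**5. Other outcomes.** Weeks 4, 12 and 24, assumed correlations 0.45–0.78, slopes 0.2–0.6 per 10 points, true difference -7.5; the shift is measured without fitting an MMRM. WOMAC Function: 0.03–0.69 toward zero (both arms), 0.5–2.2 in either direction (one arm), SE 2.28. Patient Global, with SDs from the initial sample-size section: 0.04–0.78 and 0.6–2.5, SE 2.46.

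**6. Tipping point.** At 10% missing, each 0.5 step moves the estimate 0.10 × 0.5 = 0.05. From -0.80 with SE 0.22, significance is lost after a move of 0.80 − 1.96 × 0.22 = 0.37, a shift of 0.37/0.10 = 3.7. In simulated trials with an estimate near -0.80 the median first non-significant step was 4.0 (5th–95th percentile 3.0–5.0); near -0.5 it was 1.0.

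**The case against.** The strongest reply is that no imputation under missing-at-random can test missing-at-random, and that the proposed replacement nearly duplicates the primary analysis. When the Toeplitz form is true, sequential imputation lies within 0.001 of the MMRM. This stands. The gain is narrower: a tipping point that departs from the MMRM's own assumption, and a check on the covariance form. With the SD rising from 1.6 to 2.4 over the 12 weeks, sequential imputation stayed within 0.003 of the full-data estimate, while the Toeplitz MMRM was up to 0.054 off.

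The design also works against differential dropout: one irreversible injection, no tolerability problems in prior trials, rescue allowed, no automatic discontinuation for prohibited therapy, and diary surveillance. This too stands, and it is why the one-arm scenarios are called extreme.

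Two stronger readings are tempting, and the documents do not support them:

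- A reader might infer that the tipping point stops at the observed difference, say 0.8, and so cannot reach the one-arm scenarios. SAP 7.1.6.1 steps the shift until the conclusion is overturned. The sentence "An implausible shift parameter would be higher in magnitude than the observed difference in mean change in the associated outcome" only labels how plausible the tipping shift is. At -0.80 the exercise would run to about 3.7.
- A reader might infer that treatment group is left out of the imputation, which would shrink the estimate by about the missing fraction (hypothetically -0.80 × 0.90 = -0.72). The only displayed formula conditions on group and nothing says it is omitted, so this warrants no more than listing the variables.

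**Conclusion.** The concern holds as a minor weakness confined to the sensitivity analysis. On its natural reading, 7.1.6 makes Sensitivity 1 a complete-case baseline-adjusted ANCOVA in expectation, under a stricter assumption than the MMRM. A difference between the two would be hard to interpret, and whether the tipping point runs, and where it starts, depends on that result.

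For Pain NRS with 10% missing, the one-arm range of 0.05 to 0.23 is about a quarter of the planned SE of 0.22 up to roughly one SE. The same-mechanism shift, at most about 0.085, is under half of one SE. These sizes rest on assumed correlations and dropout slopes that neither document states, and on group being in the imputation model.

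It would be wrong to infer that the primary result is biased. The primary and secondary MMRMs and the fixed-sequence tests do not use these imputations. The tipping point also remains a valid stress test for data missing not at random.

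**What to change.** In SAP 7.1.6, list the PROC MI variables and impute by treatment arm in two steps:

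1. Fill intermittent gaps by MCMC with the monotone option, using baseline and post-baseline values of the same outcome.
2. Impute the rest by monotone sequential regression on baseline and earlier post-baseline values of that outcome. For Pain NRS, use the earlier weekly averages, reduced to a subset if collinearity prevents convergence. For WOMAC and Patient Global, use Week 4 for Week 12, and Weeks 4 and 12 for Week 24.

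Run the same ANCOVA and tipping point on those datasets, so that the tipping point departs from the assumption the MMRM makes. The SAP was signed in October 2021; if the data are already unblinded, add this as a labelled supplementary analysis beside the planned one.

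The cost is revised SAP wording and slightly more programming, on data already collected. The downside is a more complex imputation model, chiefly for Pain NRS, where many correlated weekly averages enter with about 250 subjects per arm.

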9. EFFICACY ANALYSIS

The statistical hypotheses being tested in this study are:

1. The least squares estimate of improvement from baseline in Pain NRS at Week 12 is greater for subjects who received SM04690 compared to placebo.
2. The least squares estimate of improvement from baseline in WOMAC Function at Week 12 is greater for subjects who received SM04690 compared to placebo.
3. The least squares estimate of improvement from baseline in Pain NRS at Week 24 is greater for subjects who received SM04690 compared to placebo.
4. The least squares estimate of improvement from baseline in WOMAC Function at Week 24 is greater for subjects who received SM04690 compared to placebo.
5. The least squares estimate of improvement from baseline in Patient Global Assessment at Week 12 is greater for subjects who received SM04690 compared to placebo.
6. The least squares estimate of improvement from baseline in Patient Global Assessment at Week 24 is greater for subjects who received SM04690 compared to placebo.

The familywise error rate will be controlled in the strong sense using the closed, fixed sequence testing method (Dmitrienko, Tamhane, & Bretz, 2010). All hypothesis tests will be evaluated in the sequential order as listed above. Although formal hypothesis testing will stop once the first non-significant result is achieved (i.e. $p > 0.05$), all subsequent results and p-values will still be reported for reference; however, no conclusion of statistical significance will be drawn from these results.

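### Ten imputations leave avoidable Monte Carlo error in the MI sensitivity p-value near 0.05, and that p-value decides whether the tipping-point analysis runs and where it tips

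*SAP*

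**What the plan says.** SAP 7.1.6 gives multiple imputation a supporting role: "Sensitivity analysis will be performed using multiple imputation (MI) for the primary and secondary endpoints". Missing values are predicted by regression on the outcome's baseline and are "imputed independently for each timepoint", so intermediate weeks do not reduce the missing information. On the number, the section says "A total of 10 imputation datasets will be created" and cites convention as the reason. Pooling follows Rubin's rules with total variance 1.1B + Ū, "where B is the between imputation variance and U is the within imputation variance", and a divisor of 9 in B. The section adds: "Imputations will be performed with a seed of 469010".

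Appendix 3 lists this as Sensitivity 1 for the primary endpoint and for each secondary endpoint that is formally tested, the treatment difference being estimated "using baseline-adjusted ANCOVA with missing data imputed using the MI method; followed by tipping point analysis". SAP 7.1.6.1 sets the condition for the second stage: "The tipping point exercise will be conducted only for MI analysis(es) that is/are statistically significant under the MAR assumption". The tipping point is the shift at which significance is lost. Shifts move in steps of 0.5 for Pain NRS and 5 for WOMAC and Patient Global. A tipping shift larger than the observed treatment difference counts as implausible, and the MI result is then called robust.

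The main analyses (SAP 9.2.1 and 9.3.1) are MMRM on the FAS. The fixed sequence in SAP 9, where "formal hypothesis testing will stop once the first non-significant result is achieved", belongs to those analyses.

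**The concern.** The usual argument for a small number of imputations (m) concerns the efficiency of the estimate. It says little about how far a p-value moves when the imputations are redrawn. This plan puts the MI p-value against 0.05 twice: once to decide whether the tipping-point analysis is done, and again at each shift to locate the tip. Near 0.05, imputation noise can settle either step. At stake is the planned check of the missing-at-random assumption on which the MMRM rests. A borderline MI result could miss its tipping-point analysis, or tip one grid step earlier or later, because of the draw and not the data. The plan has no rule that raises m near 0.05. It mentions error estimates of the imputation in general terms but does not clearly commit to a Monte Carlo error for the p-value.

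**Working it through.** **Inputs.** From SAP 5 (re-estimated Pain NRS assumptions): difference -0.8, follow-up SD 2.4, baseline SD 1.2, correlation 0.25, 225 evaluable per group, about 500 randomised, 10% dropout. From SAP 7.1.6: m = 10, imputation from baseline, Rubin pooling. Assumptions made here: values missing completely at random, in equal shares per arm; 20% missing as a second case; m = 100 as comparator. The limiting p-value is the one obtained with very many imputations (2,000 were used).

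**1. The plan's own figures.** Residual SD = 2.4 × √(1 − 0.25²) = 2.324. With 225 per group, SE = 2.324 × √(2/225) = 0.219 and 0.8/0.219 = 3.65, so power = Φ(3.65 − 1.96) = 95.5%. The SAP states 94.3%; the unadjusted SD gives 94.2%. Also 225/0.9 = 250 per arm, or 500. The inputs are sound enough to use.

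**2. Ten is adequate for the estimate.** With 250 per arm, the complete-data variance is 2 × 2.324²/250 = 0.0432. With 10% missing information, the limiting total is 0.0432/0.9 = 0.0480, so B = 0.0048. Relative efficiency is 1/(1 + 0.1/10) = 99%. The SE is √(0.0432 + 1.1 × 0.0048) = 0.2202 at m = 10 and √(0.0432 + 1.01 × 0.0048) = 0.2192 at m = 100, a difference of about 0.5%.

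**3. It is not adequate for the p-value near 0.05.** With T the total variance, the test statistic varies over seeds with

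SD(z) ≈ √{ B/(mT) + [ z(1 + 1/m)B√(2/(m−1)) / (2T) ]² }.

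- 10% missing, m = 10, z = 1.96: √(0.0099 + 0.0025) = 0.11. The central 95% range of z is 1.96 ± 0.22, or p from 0.029 to 0.082.
- 20% missing (B = 0.0108, T = 0.0551): √(0.0196 + 0.0099) = 0.172, or p from 0.022 to 0.105.

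A limiting p of 0.04 has z = 2.054, only 0.094 above 1.960. The share of seeds that cross is then about Φ(−0.094/0.112) = 20% at 10% missing and Φ(−0.094/0.172) = 29% at 20% missing. The approximation ignores the finite degrees of freedom and the skewness of B, so simulation is the better guide.

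**4. Simulation.** One fixed data set per missing rate was re-imputed by proper Bayesian regression on baseline and arm, then analysed by ANCOVA and pooled. Only the seed changed: 2,000 seeds for m = 10 and 600 for m = 100.

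| Quantity | m | 10% missing | 20% missing |
|---|---|---|---|
| Central 95% of p, limiting p 0.05 | 10 | 0.031–0.084 | 0.024–0.112 |
| | 100 | 0.042–0.059 | 0.040–0.064 |
| Seeds with p > 0.05, limiting p 0.04 | 10 | 23% | 35% |
| | 100 | 0.5% | 5% |
| Seeds with p > 0.05, limiting p 0.03 | 10 | 4% | 16% |
| | 100 | 0% | 0% |
| Seeds with p > 0.05, limiting p 0.01 | 10 | 0% | 0.1% |
| | 100 | 0% | 0% |

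Separate runs at a limiting p of about 0.04 gave 20–24% and 34–39% for m = 10, and 0–2.5% and 4–6% for m = 100. The 2.5% rests on 3 of 120 re-runs.

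**5. The tipping shift (Pain NRS, 0.5 grid).**

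- Difference -0.8, m = 10: the tip falls at 3.0/3.5/4.0 in 7/70/24% of seeds at 10% missing, and at 1.5/2.0/2.5 in 17/77/6% at 20% missing. All of these exceed 0.8, so the verdict is stable.
- Difference -0.55, 10% missing, m = 10: the tip falls at 0.5, below the 0.55 limit, in 3% of seeds.
- Difference -0.55, 20% missing: the tip falls at 0.5 or 1.0 in 56/42% of seeds with m = 10 (in about 1% the MAR result is already non-significant). With m = 100 the split is still 55/45%. Here the grid is the cause.
- Difference -0.52: robust/not robust/not run in 62/36/2% of seeds at 10% missing with m = 10, against 92/8/0% with m = 100. At 15% missing the figures are 20/71/10% against 2/98/0%. Here m matters.

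**The case against.** The strongest reply has four parts.

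- **Only a sensitivity analysis is involved.** This stands in full. A reader might infer that the trial's primary conclusion depends on a random seed. The documents do not support that: the primary and secondary tests are MMRM and use no imputation.
- **The seed is fixed in advance.** This stands in part. A reader might infer that a favourable seed could be chosen; the stated seed rules that out and makes the run repeatable. It does not make the single reported p-value closer to its limiting value.
- **Borderline results are unlikely under the plan's assumptions.** This stands. With an expected z of 3.65, the chance that p falls between 0.03 and 0.07 is Φ(−1.48) − Φ(−1.84), about 4%, and the chance that it is below 0.01 is about 86%. For true differences of 0.6 to 0.4 the first chance rises to about 11–14%.
- **The robustness verdict is usually stable.** This mostly stands. A reader might infer that it generally turns on the seed. It does so only in some borderline data sets, and in one of those examined the 0.5 grid was responsible and m = 100 did not help.

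The constants 1.1 and 9 are correct for m = 10 and are not errors. An appeal to convention does not answer the point, because more imputations sacrifice nothing statistically.

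**Conclusion.** The concern holds as a minor point about p-value stability. When the limiting MI p-value is about 0.04, ten imputations put the reported value on the other side of 0.05 in roughly a fifth to a quarter of seeds at 10% missing, and in over a third at 20%. That can switch the tipping-point analysis off. At a limiting p-value of 0.01 or below, or at the planned difference of -0.8, the effect practically disappears. The robust/not-robust verdict can also change with the seed in borderline data sets, partly because the shift grid is coarse.

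The sizes rest on the SAP's re-estimated Pain NRS assumptions and on completely random missingness. The 10% is the planning dropout; 15% and 20% are assumptions, since the documents give no observed missing rate at Week 12. Only Pain NRS was simulated. The analytic p-value ranges depend only on the fraction of missing information, so they carry over to WOMAC and Patient Global.

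**What to change.** In SAP 7.1.6, set m to at least 100 for the MI analysis, and use the same m at every shift in 7.1.6.1. Write the pooled variance as (1 + 1/m)B + Ū and the divisor in B as m − 1, so that the constants follow m. Keep the pre-specified seed. Report the Monte Carlo error of the pooled estimate and of the p-value.

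A shift grid finer than 0.5 (Pain NRS) and 5 (WOMAC, Patient Global) should accompany this, because a larger m does not cure grid coarseness.

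The figure of 100 is a judgement supported by the table above, not a value from the documents. The cost is a few lines of SAP text and seconds to minutes of computing, with no statistical loss. If the analysis has already been run, a repeat with larger m, labelled as additional, settles the matter.
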